2.2.2 Durvalumab

Durvalumab is a human monoclonal antibody (mAb) of the immunoglobulin G (IgG) 1 kappa subclass that blocks the interaction of PD-L1 (but not programmed cell death ligand-2) with

PD-1 on T cells and CD80 (B7.1) on immune cells. It is being developed by AstraZeneca for use in the treatment of cancer. (MedImmune is a wholly owned subsidiary of AstraZeneca; AstraZeneca/MedImmune will be referred to as AstraZeneca throughout this document.) The proposed mechanism of action for durvalumab is interference in the interaction of PD-L1 with PD-1 and CD80 (B7.1). Blockade of PD-L1/PD-1 and PD-L1/CD80 interactions releases the inhibition of immune responses, including those that may result in tumour elimination. In vitro studies demonstrate that durvalumab antagonises the inhibitory effect of PD-L1 on primary human T cells resulting in the restored proliferation of interferon (IFN)- γ (Stewart et al 2015). In vivo studies have shown that durvalumab inhibits tumour growth in xenograft models via a T-cell-dependent mechanism (Stewart et al 2015). Based on these data, durvalumab is expected to stimulate the patient's anti-tumour immune response by binding to PD-L1 and shifting the balance towards an anti-tumour response. Durvalumab has been engineered to reduce antibody-dependent cellular cytotoxicity and complement-dependent cytotoxicity.

To date, durvalumab has been given to more than CCI patients as part of ongoing studies either as monotherapy or in combination with other anticancer agents. Details on the safety profile of durvalumab monotherapy are summarised in Section 4.3.1 and Section 8.3.13. Refer to the current durvalumab IB for a complete summary of pre-clinical and clinical information including safety, efficacy, and PK.

2.3 Benefit/risk assessment

More detailed information about the known and expected benefits and risks and reasonably expected adverse events (AEs) of durvalumab may be found in the IB.

See Section 9.6.1 and Appendix A for information regarding the Data Monitoring Committee.

2.3.1 Potential benefits of durvalumab

Durvalumab, a human monoclonal antibody directed against human PD-L1, may offer benefit to this patient population. In the PACIFIC study, durvalumab treatment demonstrated a statistically significant (hazard ratio [HR]: 0.52; 98.9% confidence interval [CI]: 0.39, 0.70; p-value less than 0.0001) and clinically meaningful prolongation of PFS (according to Blinded Independent Central Review [BICR] assessment of RECIST 1.1) compared with placebo in patients with locally advanced, unresectable NSCLC whose disease had not progressed after platinum-based cCRT. The risk of progression or death was reduced by 48% on the durvalumab treatment compared with placebo. The durvalumab treatment demonstrated a median PFS improvement of 11.2 months when compared with placebo (the median PFS was 16.8 months in the durvalumab group and 5.6 months in the placebo group). The PFS benefit in favour of durvalumab was observed irrespective of PD-L1 expression (HR: 0.59; 95% CI: 0.43, 0.82 for less than 25% and HR: 0.41; 95% CI: 0.26, 0.65 for at least 25%).

The improvement of PFS is supported by the clinically meaningful incremental ORR of 12% over placebo (28.4% in the durvalumab group vs 16.0% in the placebo group; nominal p-value less than 0.001). The responses were durable with the median DoR not reached in the durvalumab group, compared to 13.8 months in the placebo group. TTDM was longer for the durvalumab group compared to the placebo group (HR: 0.52; 95% CI: 0.39, 0.69; nominal p-value <0.0001). The median TTDM was 23.2 months in the durvalumab group, compared to 14.6 months in the placebo group.

In addition, durvalumab treatment demonstrated a statistically significant OS benefit with clinically meaningful improvement compared to placebo (stratified HR for death, 0.68; 99.73% CI, 0.469 to 0.997; p=0.0025). The 4-year survival update demonstrated a long-term clinical benefit with durvalumab after chemoradiotherapy. Median OS were 47.5 months in durvalumab arm, compared to 29.1 months in placebo arm, with 18.4 months prolongation. The OS rate remains higher for durvalumab compared to placebo at 36 month (56.7% vs 43.6%, respectively) and 48 month (49.6% vs 36.3%, respectively) landmarks.

Please refer to the current IB for clinical experience with durvalumab.

2.3.2 Overall risks

Monoclonal antibodies directed against immune checkpoint proteins, such as PD-L1 as well as those directed against PD-1 or CTLA-4, aim to boost endogenous immune responses directed against tumour cells. By stimulating the immune system, however, there is the potential for adverse effects on normal tissues.

Most adverse drug reactions seen with the immune checkpoint inhibitor class of agents are thought to be due to the effects of inflammatory cells on specific tissues. These risks are generally events with a potential inflammatory or immune mediated mechanism and that may require more frequent monitoring and/or unique interventions such as immunosuppressants and/or endocrine therapy. These immune-mediated effects can occur in nearly any organ system, and are most commonly seen as gastrointestinal AEs such as colitis and diarrhoea, pneumonitis/interstitial lung disease (ILD), hepatic AEs such as liver enzyme elevations, skin events such as rash and dermatitis, and endocrinopathies including hypo- and hyperthyroidism.

2.3.2.1 Durvalumab

Risks with durvalumab include, but are not limited to, diarrhoea/colitis, pneumonitis/ILD, endocrinopathies (ie, events of hypophysitis, adrenal insufficiency, hyper- and hypo-thyroidism, and type I diabetes mellitus), hepatitis/increases in transaminases, nephritis/increases in creatinine, pancreatitis/increases in amylase and lipase, rash/dermatitis, myocarditis, myositis/polymyositis, other rare or less frequent inflammatory events including

neurotoxicities, infusion-related reactions, hypersensitivity reactions, and infections/serious infections.

For information on all identified and potential risks with durvalumab, please always refer to the current version of the durvalumab IB.

In monotherapy clinical studies, AEs reported very commonly include events such as fatigue, diarrhoea, nausea and vomiting, decreased appetite, and muscle and joint pain. A total of 5% to 10% of participants discontinued the drug due to an AE. Please see the current version of the IB for a detailed summary of the monotherapy data including AEs, severe adverse events (SAEs), and Common Toxicity Criteria (CTC) Grade 3 to 5 events reported across the durvalumab program.

The majority of treatment-related AEs were manageable, with dose delays, symptomatic treatment, and in the case of events suspected to have an immune basis, the use of established treatment guidelines for immune-mediated toxicity (see Section 8.4.5).

A detailed summary of durvalumab monotherapy AE data can be found in the current version of the durvalumab IB.

2.3.3 Overall benefit/risk

In summary, the potential for clinical benefit associated with inhibition of the PD-1/PD-L1 pathway, as supported by objective responses observed in earlier studies in participants with NSCLC and demonstrated in terms of PFS by a Phase III study in participants with locally advanced unresectable Stage III NSCLC after cCRT, outweighs the known and potential risks based on the AEs reported in participants treated with durvalumab and other PD-1/PD-L1 inhibitors. Thus, the benefit/risk assessment favours the conduct of this proposed study.

The safety of participants in this study will be assessed by an Independent Data Monitoring Committee (IDMC) via ongoing safety assessments periodically in accordance with the IDMC charter.

3 OBJECTIVES AND ENDPOINTS

Objectives and Endpoints

Primary objective:	Endpoint/variable:
To assess the efficacy of durvalumab treatment compared with placebo in terms of PFS in randomised participants without sensitizing EGFR mutations or ALK rearrangements (i.e. mITT)	PFS using BICR assessments according to RECIST 1.1 ^a

Key secondary objective:	Endpoint/variable:
To further assess the efficacy of durvalumab compared with placebo in terms of OS in the mITT	OS
Secondary objective:	Endpoint/variable:
To further assess the efficacy of durvalumab treatment compared with placebo in terms of PFS in all randomised participants (i.e. ITT)	PFS using BICR assessments according to RECIST 1.1 ^a
To further assess the efficacy of durvalumab compared with placebo in terms of OS in the ITT	OS
To further assess the efficacy of durvalumab compared with placebo in terms of: OS24, ORR, DoR, PFS12, PFS18, PFS2, and TTDM in the mITT, and separately in the ITT	OS24
	ORR using BICR assessments according to RECIST 1.1 ^b
	DoR using BICR assessments according to RECIST 1.1 ^b
	PFS12 and PFS18 using BICR assessments according to RECIST 1.1
	PFS2 as defined by local standard clinical practice TTDM using BICR assessments according to RECIST 1.1 ^b
To assess the PK of durvalumab	Concentration of durvalumab in blood and non-compartmental PK parameters (such as peak concentration and trough, as data allow) (sparse sampling)
To investigate the immunogenicity of durvalumab	ADA (confirmatory results: positive or negative; titres [ADA neutralising antibodies will also be assessed])
To assess symptoms and health-related quality of life in participants treated with durvalumab compared with placebo using EORTC QLQ-C30 v3 and QLQ-LC13 in the mITT, and separately in the ITT	Change in patient-reported symptoms, functioning and global health status/QoL
To investigate the relationship between a participant's baseline tumour PD-L1 expression and efficacy outcomes with durvalumab compared with placebo in the mITT, and separately in the ITT	IHC analysis of tumoural PD-L1 expression and spatial distribution within the tumour microenvironment relative to efficacy outcomes (OS, PFS, and ORR)
Safety objective:	Endpoint/variable:
To assess the safety and tolerability profile of durvalumab compared with placebo	AEs, physical examinations, vital signs, electrocardiograms, and laboratory findings

Objectives and Endpoints

Exploratory objective:	Endpoint/variable:
To investigate the relationship between a participant's CCI and efficacy outcomes with durvalumab	CCI relative to efficacy outcomes (OS, PFS, and ORR)
To explore irRECIST criteria as an assessment methodology for clinical benefit of durvalumab compared with placebo by BICR	PFS and ORR using BICR assessments according to irRECIST $^{\rm c}$
To investigate the relationship between durvalumab PK exposure and clinical outcomes, efficacy, AEs and/or safety parameters, if deemed appropriate	A graphical and/or a data modelling approach will be used to analyse durvalumab PK exposure and the relationship with clinical outcomes, efficacy, AEs and/or safety parameters, as deemed appropriate
To describe and evaluate resource use associated with durvalumab treatment and underlying disease	Health resource utilisation measures including hospitalisation, outpatient visits, or emergency department visits
To explore the impact of treatment and disease state on health state utility using the EQ-5D-5L	The EQ-5D-5L health state utility index will be used to derive health state utility based on participant reported data
CCI	
To explore the relationship(s) between a participant's biomarker status and durvalumab PK exposure and clinical outcomes before and after treatment	Biomarker status before and after treatment and durvalumab PK exposure and relationship with clinical outcomes, efficacy, AEs and/or safety parameters, as deemed appropriate
To explore potential biomarkers in residual biological samples (eg, CCI), which may influence the progression of cancer (and associated clinical characteristics) and/or prospectively identify participants likely to respond to durvalumab treatment	Correlation of biomarkers with response to durvalumab treatment and/or the progression of cancer

- The primary analysis of PFS will be based on programmatically derived PFS BICR assessment according to RECIST
 1.1. See the statistical methods section for further details.
- ^b Analysis of ORR, DoR, and TTDM will be based on BICR assessment according to RECIST 1.1. See the statistical methods section for further details.
- c Exploratory endpoints and analyses related to PFS/ORR analyses using irRECIST data may be presented outside of the main CSR.
- Note: Prior irradiated lesions may be considered measurable and selected as target lesions providing they fulfil the other criteria for measurability.

ADA Anti-drug antibody; AE Adverse event; BICR Blinded Independent Central Review; DoR Duration of response; EQ-5D-5L EuroQoL 5-dimension, 5-level health state utility index; EORTC QLQ-C30 European Organisation for Research and Treatment of Cancer 30-item core quality of life

questionnaire; IHC Immunohistochemical; irRECIST Immune-related Response Evaluation Criteria In Solid Tumors; ORR Objective response rate; OS Overall survival; OS24 Proportion of participants alive at 24 months from randomisation; PD-L1 Programmed death ligand 1; PFS Progression free survival; PFS2 Time from randomisation to second progression; PFS12 Proportion of participants alive and progression free at 12 months from randomisation; PFS18 Proportion of participants alive and progression free at 18 months from randomisation; PK Pharmacokinetic(s); QLQ-LC13 13-item self-administered questionnaire for lung cancer; QoL Quality of Life; RECIST Response Evaluation Criteria In Solid Tumors; TTDM Time to death or distant metastasis; CCI

4 STUDY DESIGN

4.1 Overall design

This study is a Phase III, randomised, double-blind, placebo-controlled, multicentre study assessing the efficacy and safety of durvalumab compared with placebo as consolidation therapy in participants with locally advanced, unresectable NSCLC (Stage III) who have not progressed following definitive, platinum-based, chemoradiation therapy.

Approximately 400 participants with locally advanced, unresectable NSCLC (Stage III) who received cCRT or sCRT will be randomised globally. These participants will be in complete response (CR), partial response (PR), or have stable disease (SD) following definitive, platinum-based, concurrent or sequential chemoradiation therapy.

Participants must have histologically or cytologically documented NSCLC and present with locally advanced, unresectable (Stage III) disease (according to Version 8 of the International Association for the Study of Lung Cancer [IASLC] Staging Manual in Thoracic Oncology. The number of participants with a sensitizing EGFR mutation (e.g., exon 19 deletion or exon 21 L858R, exon 21 L861Q, exon 18 G719X, or exon 20 S768I mutation) or ALK rearrangement will be capped at approximately 7% of the total number of participants randomised. In order to reflect global clinical practice, study will recruit at least 60% of participants who received prior cCRT. The majority of participants will be recruited in China.

Participants will be randomised in a 2:1 ratio (durvalumab to placebo) to 1 of 2 arms:

- Durvalumab (1500 mg every 4 weeks [q4w] intravenously [iv] until confirmed radiological progression, or other discontinuation criterion is met)
- Placebo (matching placebo for infusion q4w iv until confirmed radiological progression, or other discontinuation criterion is met)

Randomisation will be stratified by the level of PD-L1 expression (PD-L1 <1% or PD-L1 \geq 1%] and prior therapy (cCRT or sCRT). Participants must not have progressed following definitive, platinum-based, concurrent or sequential CRT (see Section 5.1 for details). For those participants randomised to the placebo arm, no crossover to the durvalumab arm is permitted; similarly, those participants randomised to the durvalumab arm cannot crossover to the placebo arm.

Administration of study treatment (ie, investigational product [IP] durvalumab or placebo) will commence on Day 1 following randomisation to durvalumab or placebo after confirmation of eligibility and will continue on a q4w schedule until confirmed radiological progression, initiation of alternative cancer therapy, unacceptable toxicity, withdrawal of consent, or other reasons which reaching the discontinuation criteria (Section 7.1).

Tumour assessments using computed tomography (CT)/magnetic resonance imaging (MRI) will be performed at the times specified in Table 1 and Table 2. RECIST 1.1 measurements (using BICR assessments) will be used to derive the primary variable of PFS and secondary variables of ORR, DoR, PFS12, and PFS18.

Once a participant has had objective radiological progression recorded and has discontinued study treatment, the participant will be followed up for survival status monthly at the first 4 months, and then every 2 months until death, withdrawal of consent, or the end of the study.

Once the planned statistical analyses have been performed, the analysis portion of the clinical study will have been completed. See Section 4.4 for more information on study completion.

In the event that a roll-over or safety extension study is available at the time of the final data cutoff (DCO) and database closure, participants currently receiving treatment with durvalumab may be transitioned to such a study, and the current study would reach its end. The roll-over or safety extension study would ensure treatment continuation with visit assessments per its protocol. Any participant who would be proposed to move to such a study would be given a new informed consent.

For an overview of the study design see Figure 1, Section 1.3. For details on treatments given during the study, see Section 6.1 Treatments Administered. Guidelines for the management of toxicities are described in Section 8.4.5.

For details on what is included in the efficacy and safety endpoints, see Section 3 Objectives and Endpoints.

4.1.1 Study conduct mitigation during study disruptions due to cases of civil crisis, natural disaster, or public health crisis

The guidance given below supersedes instructions provided elsewhere in this CSP and should be implemented only during cases of civil crisis, natural disaster, or public health crisis (eg, during quarantines and resulting site closures, regional travel restrictions, and considerations if site personnel or study participants become infected with SARS- CoV-2 or similar pandemic infection) which would prevent the conduct of study-related activities at study sites, thereby compromising the study site staff or the participant's ability to conduct the study. The investigator or designee should contact the study Sponsor to discuss whether the mitigation plans below should be implemented. To ensure continuity of the clinical study during a civil crisis, natural disaster, or public health crisis, changes may be implemented to ensure the safety of study participants, maintain compliance with Good Clinical Practice, and minimize risks to study integrity.

Where allowable by local health authorities, ethics committees, healthcare provider guidelines (eg, hospital policies) or local government, these changes may include the following options:

- Obtaining reconsent for the mitigation procedures (note, in the case of verbal reconsent, the Informed Consent Form (ICF) should be signed at the participant's next contact with the study site).
- Telemedicine visit: Remote contact with the participants using telecommunications technology including phone calls, virtual or video visits, and mobile health devices.

For further details on study conduct during civil crisis, natural disaster, or public health crisis, refer to Appendix I.

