1.3 Number of subjects

The study will randomise approximately 400 patients in the ITT population and approximately 375 patients in the mITT population. Patients who received prior concurrent chemoradiation (cCRT) or sequential chemoradiation (sCRT) and have not progressed following definitive chemoradiation therapy will be randomised in a 2:1 ratio to receive durvalumab and placebo.

Randomisation will be stratified by the level of PD-L1 expression (PD-L1 <1% or PD-L1 ≥1%) and prior therapy (cCRT or sCRT).

The number of patients with sensitizing epidermal growth factor receptor (EGFR) mutation or anaplastic lymphoma kinase (ALK) rearrangement randomised will be capped at approximately 7% of the total number of patients randomised. In order to reflect global clinical practice, study will recruit at least 60% of patients who received prior cCRT. The majority of patients will be recruited in China.

Eligible patients will be in complete response (CR), partial response (PR), or have stable disease (SD) following definitive, platinum-based, cCRT or sCRT.

The primary objective of this study is to assess the efficacy of durvalumab compared with placebo in terms of PFS per RECIST 1.1 as assessed by BICR in the mITT population. The key secondary endpoint (i.e., included in the multiple testing procedure) is OS (mITT).

The primary PFS (mITT) analysis data cut-off (DCO) will occur when whichever of the following conditions have been met first:

- Reaching approximately [CCI] BICR progression-free survival events across the durvalumab and placebo treatment arms (approximately [CCI] maturity) in the mITT population

OR

- Approximately [CCI] months follow-up from last patient randomized to the study.

If the true PFS HR is [CCI] with an estimated [CCI] BICR PFS events in the mITT, the study will provide at least [CCI] power to demonstrate a statistically significant difference for PFS with [CCI] this translates to approximately a [CCI]-month benefit in median PFS over [CCI] months on placebo. The smallest treatment difference that would be statistically significant is a HR of [CCI]. A recruitment period of approximately [CCI] months and a follow-up period of [CCI] months are expected for the PFS (mITT) final analysis.

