2.1.2 Modified intent-to-treat set

The mITT set will include all randomised patients in the ITT set who are without sensitizing EGFR mutations or ALK rearrangements. Unless otherwise specified, the mITT set will be used as primary population for all efficacy analyses (including PROs). Treatment arms will be compared based on randomised study treatment, regardless of the treatment actually received.

Information on EGFR/ALK status will be based on eCRF data. If a patient has EGFR/ALK valid results from both local and central laboratories, then results from central laboratories will be used.

China mITT set

A subset of the mITT set including only those patients without sensitizing EGFR mutations or ALK rearrangements from sites located in mainland China.

The other country/region mITT set may be planned since the analysis based on country/region mITT set may be performed per the request from local health authority.

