 - Most recent sample “sampled date” should be used, unless this sample is unevaluable, in which case most recent evaluable sample is used
 - For multiple evaluable samples with the same sampled date, the sample with the highest PD-L1 % tumour membrane staining result should be used
- EGFR status (positive vs negative) - only applicable for analyses in the ITT set
- ALK status (positive vs negative) - only applicable for analyses in the ITT set
- EGRF or ALK status (positive vs negative) - only applicable for analyses in the ITT set

- Histology (squamous vs. non-squamous) WHO performance status at baseline (normal activity [PSTAT=0] vs restricted activity [PSTAT=1])
- Smoking (smoker vs. non-smoker [never smoked])
 - Patient is categorised as smoker if there exists a record in SU_NIC with any of the following options for “What type of substance was used?” 'Cigarettes', 'Cigarillos', 'Cigars', 'Pipe Tobacco', 'Tobacco for Smoking'. Else patient is a non-smoker. Non-smoker is a patient that has never smoked.
- Race (White, Black/African-American, Asian, Other [Native Hawaiian/Pacific Islander or American Indian/Alaska Native or Others])
- Race (Asian vs. non-Asian).

The subgroup analyses for the stratification factors will be based on the values entered into the IVRS, all other factors will be based on values recorded on the eCRF as indicated above.

Unless noted above, patients with unknown or missing level of baseline variables will be excluded from subgroup analyses.

Other baseline variables may also be assessed if there is clinical or biological justification or an imbalance is observed between the treatment arms. The purpose of the subgroup analyses is to assess the consistency of treatment effect across expected prognostic factors and/or predictive factors.

No adjustment to the significance level for testing of the subgroup and sensitivity analyses will be made since all these subgroup analyses will be considered exploratory and may only be supportive of the primary analysis of PFS. For each subgroup, the HR (for the treatment comparisons of interest) and 95% CI will be calculated from a Cox proportional hazards model that contains treatment. The Cox models will be fitted using SAS® PROC PHREG with the Efron method to control for ties, using the by statement to obtain HR and 95% CI for each subgroup level separately. These will be presented on a forest plot including the HR and 95% CI, along with the results of the overall primary analysis.

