4.2.14 China Cohort Analyses

Per China National Medical Products Administration's (NMPA) guidance, in addition to the evaluation of the global cohort data for primary, secondary and safety objectives, evaluation of consistency in efficacy and safety between the China subgroup and the overall global cohort is required to facilitate the benefit-risk assessment for China patients.

The efficacy and safety data for the China cohort are summarised and analysed using the same methodology as described above for the overall global population.

All statistical analyses in the China cohort will be considered as exploratory, and therefore no alpha is assigned to the efficacy assessment for this cohort.

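### China consistency is assessed against an overall cohort that is mostly China, which shrinks any regional difference; no China versus non-China contrast is firmly planned

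*Protocol*

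**What the plan says.** Protocol 4.1 states "The majority of participants will be recruited in China"; SAP 1.3 repeats it. Neither document gives a percentage.

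SAP 4.2.14, citing Chinese regulatory guidance, says "evaluation of consistency in efficacy and safety between the China subgroup and the overall global cohort is required", to support the benefit-risk assessment for patients in China. The China cohort is analysed by the same methods as the global population. The analyses are exploratory, and "therefore no alpha is assigned to the efficacy assessment for this cohort". The section sets no criterion for consistency.

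SAP 2.1.1 to 2.1.3 define China versions of the ITT, mITT and safety sets. The China mITT set is "A subset of the mITT set including only those patients without sensitizing EGFR mutations or ALK rearrangements from sites located in mainland China". No complement is defined. For elsewhere the SAP says only "The other country/region mITT set may be planned", tied to a health authority's request, with parallel wording for the ITT and safety sets.

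The PFS subgroup list in SAP 4.2.1, which SAP 4.2.2.1 carries over to OS if there are enough events, includes race as Asian versus non-Asian but not region. Region is named only among covariates that may enter the adjusted Cox model, as a main effect. The interaction tests in 4.2.1 cover the stratification factors, PD-L1 level and prior therapy. Randomisation is not stratified by region.

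**The concern.** A part is being compared with a whole that it dominates. Any true difference between China and the other sites also moves the overall estimate towards China, so the two columns sit closer together than the two regions do. Elsewhere the SAP assesses consistency of effect with disjoint levels: concurrent versus sequential chemoradiation, male versus female, stage IIIA versus IIIB/C. China is the exception.

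What is at stake is how regional heterogeneity is read in an exploratory but regulator-facing analysis. A reader shown a China HR close to the overall HR may take that as evidence of regional agreement when much of the closeness is built in. The same holds for adverse event percentages, where the shrinkage within an arm is one minus China's share of that arm's patients.

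**Working it through.** **Inputs from the documents.** China is the majority of participants, with no figure. On size, SAP 1.3 says "The study will randomise approximately 400 patients in the ITT population and approximately 375 patients in the mITT population". On allocation, Protocol 4.1 says "Participants will be randomised in a 2:1 ratio (durvalumab to placebo) to 1 of 2 arms".

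**Assumptions.** The planned PFS events, HR and power are redacted in the public copies, so no design figure can be reproduced here. I take f, China's share of the events, from 0.51 to 0.9. I take 225 to 262 PFS events (60% to 70% of 375), with 260 for the single worked interval. All HRs below are illustrative. Event share is not headcount share: the protocol synopsis expects China to start enrolling about a year after the rest of the world, so f may be below China's share of patients.

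**Step 1, the shrinkage.** The overall log HR is approximately the information-weighted mean of the two regions:

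logHR(all) = f × logHR(China) + (1 - f) × logHR(rest)

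so logHR(China) - logHR(all) = (1 - f) × [logHR(China) - logHR(rest)].

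**Step 2, two examples at f = 0.75.**
- China 0.60, rest 1.00: logHR(all) = 0.75 × (-0.511) = -0.383, HR 0.68. China/overall = 0.60/0.68 = 0.88; China/rest = 0.60.
- China 0.85, rest 0.50: logHR(all) = 0.75 × (-0.163) + 0.25 × (-0.693) = -0.295, HR 0.74. China/overall = 1.14; China/rest = 1.70.

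**Step 3, across f, for no effect in China (HR 1.0) and HR 0.5 elsewhere (China/rest = 2.00).** The last three columns come from 400,000 normal draws per scenario, with var(logHR) = 4.5/events, since 1/[(2/3)(1/3)] = 4.5. The two readings of consistency are mine, not the SAP's: (a) China keeps at least half of the overall log HR, given an overall HR below 1; (b) the overall HR lies inside China's 95% CI.

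| f | Visible share | Overall HR | China/overall | Passes (a) | Passes (b) | Power, two-sided 5% interaction test |
|---|---|---|---|---|---|---|
| 0.51 | 49% | 0.71 | 1.40 | 12–14% | 56–64% | 69–75% |
| 0.6 | 40% | 0.76 | 1.32 | 14–16% | 69–76% | 67–74% |
| 0.7 | 30% | 0.81 | 1.23 | 18–20% | 88–91% | 61–68% |
| 0.8 | 20% | 0.87 | 1.15 | 26–29% | about 99% | 50–56% |
| 0.9 | 10% | 0.93 | 1.07 | 46–49% | about 100% | 31–36% |

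In the reverse case (China 0.5, rest 1.0), reading (a) passes essentially always.

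**Step 4, precision of the disjoint contrast.** SE of the log ratio = sqrt[4.5/(D f) + 4.5/(D(1 - f))]. With D = 260 and f = 0.75: sqrt(4.5/195 + 4.5/65) = 0.304. exp(1.96 × 0.304) = 1.8, so the 95% CI is the estimate times or divided by 1.8.

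**Step 5, is information lost?** No. By step 1 the China-minus-overall difference is a fixed multiple of China-minus-rest, so with the covariance handled correctly the two z statistics are equal. The side-by-side display does not show that covariance. In step 4's setting China's own SE is sqrt(4.5/195) = 0.152, while the SE of China minus overall is 0.25 × 0.304 = 0.076, so judging by China's interval uses a yardstick twice too wide.

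**The case against.** The strongest reply is that SAP 4.2.14 does what it sets out to do. Its stated purpose is consistency with the overall cohort, under authority guidance and for China's benefit-risk assessment; it does not claim to compare China with the rest of the trial. China gets its own full efficacy and safety analyses, so a weak effect or excess toxicity there appears undiluted in China's own HR, interval and adverse event tables. Adverse event counts are additive, so non-China counts follow by subtraction. Race is a planned disjoint split, the subgroup list is open-ended, and recruitment is tabulated by region (SAP 4.2.11). The analysis carries no alpha, and the disjoint contrast has little power: for China 0.8 against 0.5 elsewhere, 38–43% at f = 0.51 and 17–19% at f = 0.9.

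Most of this stands, and it limits the point. It does not remove it. Race is not region: Asian participants enrolled outside China would blur the split, and it does not reach the adverse event tables. The open-ended list and the other-region sets are discretionary. A main effect for region adjusts the HR without asking whether the effect differs. Low power argues for estimation and against a test; it does not argue for the part-versus-whole display.

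A reader might infer that China will look consistent whatever the data, or that the plan cannot show disagreement. The documents do not support that. The SAP sets no pass/fail rule, so nothing obliges a conclusion of consistency. Near a bare majority about half of the log difference stays visible, and a null effect in China would usually fail a 50%-retention reading (column (a) above). The stronger statement comes close to true only when China's share is about 80% or more and consistency is judged by whether the overall HR falls in China's interval, or when China is the region that responds better.

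**Conclusion.** The point holds as a limited one. The comparison in SAP 4.2.14 understates a regional difference in log HR by the factor (1 - f), and no China versus non-China set, subgroup or treatment-by-region term is firmly planned. The algebra does not depend on the assumed HRs or event counts. Its size depends on f, which the documents do not give and which late enrolment in China could lower. Primary PFS, OS and the testing hierarchy are untouched. This is a cheap improvement to an exploratory analysis.

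**What to change.** - Keep the China and overall columns that the authority requires.
- In SAP 2.1.1 to 2.1.3, define the non-China complements of the ITT, mITT and safety sets.
- Add region (mainland China versus rest of world) to the PFS and OS subgroup lists in SAP 4.2.1 and 4.2.2.1.
- In SAP 4.2.14, report the China and non-China HRs for PFS and OS, and their ratio with a 95% CI from a Cox model with treatment, region and treatment-by-region. Label this exploratory estimation without alpha, with no pass/fail reading.
- Add a non-China column to the key adverse event tables.

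The change is best fixed before the PFS data are unblinded, since SAP 5.1 says the study is unblinded at that analysis.

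The cost is SAP wording and a few outputs from data already collected. The drawback is imprecision. At an assumed 260 events, the non-China set would have 65 events at f = 0.75 but only 26 at f = 0.9, close to the 20-event minimum in SAP 4.2.1, below which only descriptive summaries would be given.
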